5.7 Stratification Factors

1. Age
 - a) Men ≤ 70 years
 - b) Men > 70 years
2. Race
 - a) Black or African American
 - b) Other
3. Baseline Prostate Biopsy
 - a) 0-12 months prior to pre-registration
 - b) > 12-24 months prior to pre-registration

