11.0 STATISTICAL CONSIDERATIONS

11.1 Randomization

Patients will be randomized with equal probability to receive the dietary intervention (experimental arm) or dietary information (control arm). A total of 464 patients will be enrolled to this trial, 232 patients per arm. The study will take a total of 5 years: about 3 years of accrual with an expected accrual rate of 15 patients per month, and 2 years of follow-up for each patient.

Stratification factors: Randomization will be stratified by age (≤ 70 years vs. > 70 years), race (African American vs. Other) and baseline prostate biopsy (0-12 months prior to registration vs. >12 -24 months prior to registration).

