11.2 Design

Each patient will be followed for 24 months, and PSA will be evaluated every 3 months starting from baseline. Prostate biopsies are taken at baseline and 24 months.

The primary outcome of interest in this prevention trial is disease progression defined by (a) PSA doubling time (PSADT) < 3 years, (b) PSA ≥ 10 at any time, or (c) Gleason sum on repeat biopsy ≥ 7 for men younger than 70 years and $\geq 4+3 = 7$ for men 70 years or older. These criteria are drawn from one of the largest active surveillance studies to date, the Toronto cohort (12). Data from this cohort indicate that approximately 20% of patients on active surveillance will progress by these criteria: 14% by PSA doubling time and 8%-10% by Gleason score.

Thus, using the log-rank test with a two-sided $\alpha = 5\%$, a sample size of 418 will provide 80% power to detect a difference in progression rate (PGR) of 20% in the control and 10% in the experimental arm during 24 months of follow-up. Under the exponential distributions for the time to progression, the 2-year PGR of 20% vs. 10% corresponds to a hazard ratio (HR) of 2.118. Assuming 10% of dropout rate (including patients who are treated before progression), a total of 464 patients will be enrolled to this trial.

Centralized pathology review will be conducted on the tissue specimens of the first 50 patients. From an analysis of grading by community vs. Johns Hopkins pathologists, Gleason grading of adenocarcinoma in prostate needle biopsy tissue (106), Gleason score was changed from 3+4 by community review to 4+3 by Johns Hopkins review for about 14% of men and from 6 or below to 7 or above for about 8% of men. Assuming about 30% of men in this study will be >70 years old and these two types of changes occur uniformly over the whole range of age, we believe that no more than 10% of men will become ineligible for the study by the centralized pathology review. We will consider increasing the sample size by a maximum of 10% depending on the proportion of men who become ineligible by central pathology review.

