11.3 Analysis

The proportion of men who become ineligible by central pathology review will be estimated for each arm. The primary analysis will be done using data from eligible subjects, especially using Gleason scores from central review. However, all statistical analyses will be conducted for the data sets from eligible patients only, as well as all patients randomized in the sensitivity analysis.

Progression: PSADT will be calculated as \log_2 divided by the slope (the least squares estimator) of \log (PSA) observations over time using all available PSA measurements, starting from the time point at which we have three PSA measurements (i.e. the first

PSADT of a patient is calculated at month 6 using the PSA measurements collected at months 0, 3 and 6 if there are no missing PSA measurements.” In order to avoid any miscalculation, the PSADT will be calculated at the Alliance Statistics and Data Center, not by each individual site.

Time to progression data will be analyzed using the log-rank test for univariable analysis and the Cox’s proportional hazards regression for multivariable analysis adjusting for the stratification factors and other prognostic factors. For the patients who proceed to treatment with surgery, radiation, local ablative therapy or hormonal therapy before progression within the 2-year follow-up period, the progression time will be censored at the time of withdrawal for treatment.

A recent study in a similar cohort of men undergoing active surveillance (102) reported that PSA kinetics was not closely associated with progression on subsequent surveillance biopsies. In order to address this issue, as a secondary analysis, we will also compare time to progression defined only by Gleason sum on repeat biopsy ≥ 7 for men younger than 70 years and $\geq 4+3 = 7$ for men 70 years or older. Because of decreased number of events, the log-rank test using this definition of time to progression may not have enough power. For example, if the 2-year PGR for the control arm is only 10% by this new definition, then the log-rank test will have only 50% of power with 418 eligible patients with events or full 2 years of follow-up.

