11.4 Interim Analysis

11.4.1 Primary Endpoint

At each interim analysis, superiority and futility tests on PFS will be conducted as follows.

Superiority: A superiority test is to test if the experimental arm has a longer PFS than the control arm. The first interim analysis for superiority will be conducted when 80 patients progress or complete the 2 years of follow-up. With 6 months of run-in period and a monthly accrual of 15 patients, this will occur at approximately 33 months. After this time, interim analyses will be conducted every six months corresponding with scheduled meetings of the Alliance Data and Safety Monitoring Board (DSMB). The final analysis will be conducted 2 years after the completion of accrual. With the expected study plan, there should be about 4 or 5 interim analyses before the final analysis. The superiority testing during the interim analyses will be using one-sided $\alpha=0.0025$. (A one-sided p-value smaller than 0.5 and a test statistic larger than 0 imply the superiority of the experimental arm.) The final analysis will be using one-sided $\alpha=0.025$. Due to the relatively small number of interim analyses and the small alpha spending at each interim analysis, the overall type I error rate will not be much larger than the nominal one-sided $\alpha=0.025$ (107).

Futility: Futility testing will be conducted at the time of each interim analysis scheduled for a superiority test. We will consider stopping the study early due to futility if the 1-sided p-value is larger than or equal to 0.5 (or the standardized log-rank test statistic is smaller than 0) at any interim analysis.

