11.4.2 Progression Rate

The power of the log-rank test depends on the PGR in the two arms. An interim analysis will be conducted when 400 patients are enrolled on the study to check if the specified 20% of 2-year PGR is accurate or not. At the interim analysis, the 2-year PGR of the control arm will be estimated. If the estimate is smaller than 20%, we will recalculate the sample size using the estimated 2-year PGR for the control arm, $HR=0.472$, two sided $\alpha=0.05$ and a power of 80% and consider increasing the sample size by a maximum of 20% of the current sample size. For example, if the estimated 2-year PGR for the control arm is 18%, then we need 466 eligible patients (about 11% increase from 418 eligible patients). In case the observed progression rate is so low that a maximum of 20% increase in sample size does not guarantee a reasonable power for the primary endpoint, we will consider suspending the study for revision.

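### The log-rank test leaves out the randomization strata, and the carotenoid and diet comparisons do not use baseline as a covariate: a valid plan that gives up some precision at no saving

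*Combined protocol and SAP*

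**What the plan says.** Section 11.1 states that "Randomization will be stratified by age" and also by race and by the timing of the baseline biopsy, which makes eight cells. The log-rank test then does most of the work on the primary endpoint:

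- Section 11.2 derives the sample size "using the log-rank test with a two-sided" 5% level.
- Section 11.3: "Time to progression data will be analyzed using the log-rank test for univariable analysis". The same sentence goes on to a Cox model, a "multivariable analysis adjusting for the stratification factors" and other prognostic factors.
- Section 11.4.1 allows a futility stop if "the standardized log-rank test statistic is smaller than 0".
- Section 11.4.2 bases the sample-size re-estimation on it: "The power of the log-rank test depends on the PGR in the two arms".

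Strata are not mentioned for the log-rank test in any of these places.

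For carotenoids, item (1) in Section 11.3 compares the arms by a two-sample t-test. It has no baseline term and does not say which visit, or whether level or change, is tested. Items (2) and (3) do adjust for the stratification factors. Dietary intake is compared as increase from baseline, by t-test, at 12 and 24 months. Plasma is required of all registered men and is first drawn at preregistration (Sections 6.2 and 8.4). Completing the three run-in recalls is a condition of registration (Section 4.2.1).

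Biopsy timing is banded in Section 5.7 as "0-12 months prior to pre-registration" against the following 12 months, whereas the schema and Section 11.1 count from registration.

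**The concern.** When randomization is stratified on prognostic factors, the arms are balanced on them by design, but an unstratified log-rank test still treats that variation as noise. It then tends to be conservative and loses some power. The loss would apply to the final test, to the interim looks and to the futility rule. The documents give some reason to think the factors are prognostic: the Gleason progression threshold differs by age (Section 11.2), and Section 1.9 cites a higher risk of lethal disease in African American men.

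For the carotenoid objective (Section 10.1.2.1) and the diet comparison, a baseline value is collected from every man. A model with baseline as a covariate is at least as precise in large samples as either a follow-up-only or a change-score t-test.

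Any analysis that uses the strata, including the Cox model already planned, also needs a single definition of the biopsy-timing factor.

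**Working it through.** **1. The plan's own figure.** HR = ln(0.9)/ln(0.8) = 0.472, inverse 2.118, as stated. Freedman's formula gives (1.960 + 0.842)² × (1.472/0.528)² = 7.85 × 7.78 ≈ 61.1, rounded up to 62 events. With a mean progression rate of 15%, 62/0.15 = 413.3, so 414 men against the stated 418. Then 418/0.9 = 464.4, against 464. At 418 men, 418 × 0.15 = 62.7 events are expected and Freedman power is 81.0%. Neither figure needs to change.

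**2. Log-rank test by simulation** (40,000 trials per cell; Monte Carlo SE for power 0.2 points).

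From the documents: n = 418; HR 0.472 within strata; 20% control progression at 24 months; PSA every 3 months; 30% of men over 70 (Section 11.2); 54/464 Black men (Section 1.9). Section 11.2 gives about 20% progression in total, "14% by PSA doubling time and 8%-10% by Gleason score", so (20 − 14)/20 = 30% of events were placed at the month-24 biopsy, with 0% and 45% (9/20) as alternatives.

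Assumed: permuted blocks of 4, a 50/50 biopsy-timing split, and the same hazard ratio for each factor.

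| HR per factor | Power: unstratified | 8 strata | 5 strata (Black men pooled) | Type I: unstratified | Type I: 8 strata |
|---|---|---|---|---|---|
| 1 | 82.5% | 82.5% | 82.5% | 5.3% | 5.2% |
| 1.5 | 82.2% | 82.4% | 82.5% | 4.9% | 5.1% |
| 2 | 81.3% | 82.5% | 82.4% | 4.2% | 4.9% |
| 3 | 78.9% | 82.5% | 81.7% | 3.5% | 5.0% |

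HR 3 on all three factors is extreme: control progression then runs from 6% to 82% across strata.

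Gains from 8 strata under other assumptions, in points of power at HR 1, 1.5, 2 and 3:

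- 45% of events at month 24: 0, 0.3, 1.2, 3.3.
- No events clustered at month 24: −0.2, 0.3, 1.1, 4.0.
- 80/20 biopsy split, 30% at month 24: −0.2, 0.2, 0.9, 3.4.

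In the base case the two tests disagree about p < 0.05 in 0.9%, 1.3%, 2.3% and 4.8% of trials.

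**3. Sparse cells.** Each of the two cells of Black men over 70 holds 418 × 0.30 × 54/464 × 0.5 ≈ 7 men and, at 15%, about 1 event. Pooled, Black men form one stratum of 418 × 54/464 ≈ 49 men and about 7 events.

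**4. Carotenoids and diet.** Let r be the correlation between baseline and follow-up, which the documents do not give. With equal variances, the variance of the adjusted estimate is (1 − r²) times that of a follow-up-only t-test and (1 + r)/2 times that of a change-score t-test.

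| r | Reduction against follow-up only | Reduction against change score |
|---|---|---|
| 0.3 | 9% | 35% |
| 0.5 | 25% | 25% |
| 0.7 | 49% | 15% |
| 0.8 | 64% | 10% |

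For scale, Table 2 in Section 1.7 gives a pilot difference in total carotenoids of (2.79 − 2.21) − (2.32 − 2.24) = 0.50, with p = 0.02 and n = 45 and 23. If that p came from a change-score test, the SE is 0.50/2.326 = 0.215 and the SD of change is 0.215/√(1/45 + 1/23) = 0.84. The SD of level is then 0.84/√(2(1 − r)).

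With 209 men per arm:

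- Pilot effect, r = 0.7: SD of level 1.08; SE 1.08 × √(2/209) = 0.106; z = 4.7 unadjusted and 4.7/√0.51 = 6.6 adjusted. The 95% CI half-width falls from 0.21 to 0.15.
- Half the pilot effect (0.25): power is 86% follow-up-only against 94% adjusted at r = 0.5, and 66% against 91% at r = 0.7. A change-score test gives 86% at either r.

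**5. Biopsy-timing anchor.** Section 5.4 puts the run-in at about 3 to 4 weeks from pre-registration; a second attempt could stretch it to about 8 (assumed). If biopsy dates are spread evenly over 24 months (assumed), 3, 4 and 8 weeks are 2.9%, 3.8% and 7.7% of that span, or 13, 18 and 36 of 464 men on different sides of the 12-month cut under the two anchors. As many again would be eligible at pre-registration (Section 4.1.1) but past 24 months at registration, and so in neither band. With an 80/20 split, even within each year, the first count becomes 0.8 × 3/52.2 × 464 ≈ 21 to 0.8 × 8/52.2 × 464 ≈ 57, and the second 0.2 × 3/52.2 × 464 ≈ 5 to 0.2 × 8/52.2 × 464 ≈ 14.

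**The case against.** The strongest reply is that this is a preference, not a defect. The unstratified test is valid, the sample size is right for it, and a strata-adjusted Cox estimate of the primary effect is already planned in the same sentence. The log-rank gain rests on assumed prognostic strength and is close to nothing up to HR 2. All of that stands, and it is why the point is minor.

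Two technical replies also have force:

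- Holding HR 0.472 within strata raises the overall experimental progression rate to 10.5% at factor HR 3, so part of the fall to 78.9% comes from calibration. Recalibrated to 20% against 10% overall (5,000 runs, SE about 0.5 points), power is 83.0% unstratified and 84.0% stratified at HR 2, and 84.7% and 87.6% at HR 3. The level of power changes; the gain of about 1 and 3 points does not.
- The 9% to 64% saving for carotenoids applies only if follow-up levels are tested. On a change-score reading, the contrast at half the pilot effect and r = 0.7 is 86% against 91%. The plan does not say which is meant, which is itself a reason to specify the model.

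The type I error of 5.3% at HR 1 is slightly above nominal, but the stratified test shows 5.2%, so omitting the strata is not the cause. Finally, the carotenoid comparison is correlative and diet intake is not a listed objective in Section 2, so neither bears on the primary conclusion.

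**Conclusion.** The concern holds as a minor efficiency point. Ignoring the strata does not raise the false-positive risk; if the factors are prognostic, it makes the test somewhat conservative. Stratifying gains 0 to 1.2 points of power up to HR 2 per factor, and 3 to 4 points only at HR 3. The baseline-adjustment gain is potentially larger: over r = 0.3 to 0.8, a variance reduction of 9% to 64% for carotenoids (if levels are tested) and 35% down to 10% for diet. At the pilot effect the carotenoid conclusion would be the same either way; at about half that effect the gain becomes material. Stratum effects, correlations, block size and biopsy split are all assumed. The conflicting biopsy-timing anchor is a plain inconsistency in the text, whatever view is taken on efficiency.

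**What to change.** - Stratify the log-rank test by the factors as recorded at randomization, at the interim and final analyses, with a matching stratified Cox model for the hazard ratio.
- State a pooling rule for sparse cells in advance, for example Black men as one stratum, giving five in all. This keeps nearly all the gain up to HR 2.
- Compare carotenoids and food intakes at 12 and 24 months with a linear model containing the baseline value and the stratification factors. This also settles the visit and the level-or-change question for carotenoids.
- Reconcile the biopsy-timing anchor between Section 5.7 and the schema and Section 11.1, so that the analysis strata are those used at randomization.

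The cost is SAP wording and the pooling rule; no new data are needed and 418 and 464 stand. The downside is sparse strata, which the pooling rule addresses. Because the primary and interim tests would change, the change should be made before any comparative data are examined.

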2.2 Secondary Objectives

2.2.1 To compare the incidence of active treatment (surgery, irradiation, local ablation, or androgen deprivation) in AS patients receiving dietary intervention compared to no intervention.

2.2.2 To compare prostate cancer-related anxiety in AS patients receiving dietary intervention compared to no intervention.

2.2.3 To compare health-related quality of life in AS patients receiving dietary intervention compared to no intervention.

[See Section 10.0 for correlative science objectives.]

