6.0 DATA SUBMISSION AND SAMPLE SUBMISSION

6.1 Data Submission

Forms should be submitted to the Alliance Statistics and Data Center (SDC) in compliance with the Data Submission Schedule below.

Forms must be submitted electronically using the “Submit to CALGB” button located at the bottom of the last page of each form. Any required forms, supporting documentation or amended forms that cannot be submitted electronically should be mailed directly to the Alliance Data Center for scanning and quality review at the address below:

Alliance Data Center

[Redacted address information]

For the most up-to-date forms, please visit the Alliance or CTSU web site.

Data Submission Schedule:

Form		Submission Schedule
	Pre-Registration Pre-Registration Worksheet	Submit at pre-registration
C-2010	MEAL Participant Contact Information Form	Submit to UCSD staff (See Sec. 5.2)
	Registration Registration Worksheet CALGB 70807 On Study Form	Submit within 2 weeks of registration
C-2002	CALGB 70807 Personal Habits Questionnaire	To be administered to patients at the pre-registration visit and submitted to the Alliance Statistics and Data Center within 2 weeks of registration.
C-2003	CALGB 70807 MAX-PC Form	
C-2004	CALGB 70807 Nutritional Self Efficacy Form	
C-2005	CALGB 70807 IPSS Form	
C-2023	CALGB 70807 EPIC-26 Form	
C-2007	CALGB 70807 FACT-P Form	
	During Intervention	
C-2013	CALGB 70807 Follow Up Form	Submit at 3, 6, 9, 12, 15, 18, 21, 24 months
C-2081	CALGB 70807 PSA Doubling Time Form	Submit at 6 months
C-2003	CALGB 70807 MAX-PC Form	Submit at 6, 12, 18 and 24 months
C-2005	CALGB 70807 I-PSS Form	
C-2023	CALGB 70807 EPIC-26 Form	
C-2007	CALGB 70807 FACT-P Form	
C-2004	CALGB 70807 Nutritional Self Efficacy Form	
C-2008	CALGB 70807 MEAL Study Counseling Evaluation Form	Arm A patients only: Submit at 12 and 24 months
	Post Intervention Follow-Up	
C-2013	CALGB 70807 Follow Up Form	Submit every 3 months until 2 years from date of registration (see Section 8.7)
	Other	
C-260	CALGB Remarks Addenda	Submit as needed

If a study participant chooses to withdraw from the study, submit the C-260 CALGB Remarks Addenda to the Alliance Data Center and copy by fax [REDACTED]

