8.6.1 Quality control

Quality control will be enhanced by providing the telephone counseling from a centralized location at the Moores UCSD Cancer Center, thus enabling weekly case management meetings and flexibility in scheduling. Dietary counselors will be hired based on their demonstrated communication skills, telephone manner, knowledge of food and nutrition, and their enthusiasm for achieving the study dietary targets. Counselors will complete an intensive 80-hour training program addressing the rationale for the study, protocols for conducting 24-hour dietary recalls, the principles and practice of motivational interviewing and review of a random selection of recorded calls.

All counselors will practice extensive role-playing before conducting their first coaching session. This training will be overseen by the UCSD behavior change study team; the team has been involved in a multitude of behavior change studies.

We have developed a detailed, relational database that provides counselors with a computer-assisted coaching protocol for their participant contacts. All contacts will be recorded in the database, and the database will generate the call schedule for each counselor each day. Calls will then follow a script that includes suggested question phrasing and responses to key questions inserted into the database in real time; these standardize intervention delivery. Automatic range checks will ensure quality in the dataset. At the completion of each call, the counselor will be prompted for detailed comments that can be used in the next contact. These comments will be reviewed by the supervisor as a component of performance review. Each counselor's performance will be compared to that of his or her peers, in terms of achieving dietary change toward study goals and in keeping the database complete.

The database will provide weekly management reports to focus on key aspects of study progress, including delinquent data collection. The database will help us monitor regularly scheduled study operations, to comply with aspects of the protocol. For example, study reports will be generated, as needed, to identify intervention participants who have not been contacted as scheduled in the protocol. The reports will be provided to the counselors to help keep them on schedule, and to ensure that participants with lagging performance or possibly lagging interest do not drop out of the study.

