9.6 Nutrition Self-Efficacy Scale

The Nutrition Self-Efficacy scale assesses the degree to which individuals are confident that they can control their nutrition (79). The scale assesses perceived self-efficacy, the confidence in one's ability to meet one's goals, and coping self-efficacy, defined as optimistic beliefs about one's capability to deal with barriers that arise in plans. The scale consists of 5 items rated on a 5 point Likert scale, ranging from 'very confident' to 'not confident at all'. Internal consistency was excellent (alpha coefficient = .87, n= 1,722). Evidence of validity was provided by the Nutritional Efficacy Scale correlating significantly with nutritional behavior ($r = .34$, $p < .01$) (80). Because quality of life or anxiety has not been formally evaluated in an AS population or in the setting of a randomized clinical trial among AS patients, a battery of scores will be assessed as exploratory variables, with scores at each time point and changes in scores over time assessed between the intervention and control groups using student's t-test and linear regression modeling.

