Time to Treatment: Probability to proceed to treatment within 2 years (binary observation) and time to treatment (censored time to an event observation) will be analyzed using the chi-squared test and the log-rank test, respectively. We expect that the control arm will have more patients receiving treatment and shorter time to treatment than the experimental arm because of anxiety.

QOL: Quality of life (anxiety and depression, prostate cancer symptom checklist) will be compared between the two arms. The time trajectory of QOL will be estimated using the generalized estimating equation method based on working independent correlation structure (103) and the slope of the time trajectory will be compared between the two arms (104). We will consider taking a log-transformation of QOL observations if it improves the linearity of the time trajectory of QOL. The significance of the two arm comparisons will be adjusted for multiple testing among different QOL subscales using the methodology of Bang, Jung and George (105).

Dietary Recall: Diets will be evaluated at baseline and at 12 and 24 months by a series of three separate 24-hour dietary recalls collected interactively via telephone interview. The increase (from baseline) in mean daily intakes of total vegetables, crucifers, tomato products, beans/legumes and fat will be compared between arms using a two-sample t-test at 12 and 24 months. We may consider transforming (e.g. using logarithm) the data to improve normality of the distributions and variance stabilization. Data will be catalogued and analyzed utilizing Minnesota Nutrition Data System (NDS) software (Nutrition Coordinating Center, University of Minnesota).

Plasma carotenoid analyses:

- (1) Plasma carotenoid concentrations (PCC) will be compared between the two arms using a two-sample t-test. A log-transformation of the PCC observations may be considered in order to improve the normality of the distributions and variance stabilization.
- (2) PCC will be correlated with PSADT for the patients. Descriptive analysis using scatter plots and regression analysis will be conducted. Intervention and known predictors including the stratification factors will be adjusted in multivariable analysis.

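### The planned QOL analysis (unweighted GEE, working independence) has no protection if missing forms depend on earlier scores and this differs by arm; a likelihood-based or weighted analysis would give it under missing at random

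*Combined protocol and SAP*

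**What the plan says.** Section 2.2 makes anxiety a secondary objective: "To compare prostate cancer-related anxiety in AS patients receiving dietary intervention compared to no intervention". Health-related quality of life is the next one. The anxiety, urinary, EPIC-26 and FACT-P forms are collected at pre-registration and then, in Section 6.1, "Submit at 6, 12, 18 and 24 months".

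For the analysis, Section 11.3 names the "generalized estimating equation method based on working independent correlation structure" and says that "the slope of the time trajectory will be compared between the two arms". It allows a log transformation and adjusts for multiple subscales. It does not say what is assumed about missing forms or how they will be handled.

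Two other places bear on the point. Section 9.6 says that "a battery of scores will be assessed as exploratory variables", and names t-tests and linear regression rather than GEE. Section 11.2 has the only dropout figure: "Assuming 10% of dropout rate (including patients who are treated before progression), a total of 464 patients will be enrolled to this trial".

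**The concern.** Unweighted GEE under working independence fits the trajectory to whatever scores are observed at each visit. A man with a high score at 12 months who returns nothing later simply leaves the 18- and 24-month averages, and his earlier scores do nothing to correct them. The estimated trajectory in an arm is therefore right only if, within that arm, missingness is unrelated to the scores. A likelihood-based model uses the correlation between visits to carry the earlier scores forward, and needs only missing at random.

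There is reason to think that the arms could differ. Participants are not blinded (Section 1.6). Section 11.3 expects more treatment in the control arm because of anxiety, which is the outcome being measured. Withdrawal from the diet (Section 8.7.1) can happen only in Arm A. What is at stake is the anxiety and quality-of-life comparison under objectives 2.2.2 and 2.2.3.

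**Working it through.** **1. What the 10% refers to.** Section 11.2 sizes the trial for the log-rank test on progression. The hazard ratio is ln(0.80)/ln(0.90) = 2.118, as stated. Inflating 418 for 10% gives 418/0.90 = 464.4, against the stated 464. So the 10% belongs to the primary endpoint, and it counts men treated before progression. Section 8.7.3 keeps such men in follow-up for the full two years, and the form schedule does not exempt them. The 10% is thus not a forecast of missing forms; the true rate could be lower or higher.

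**2. Inputs to the simulation.**
- From the documents: 232 men per arm (Section 11.1); visits at 0, 6, 12, 18 and 24 months (Section 6.1); slope contrast between arms (Section 11.3).
- Assumed, not in the documents: unit SD, constant within-man correlation of 0.5, 0.7 or 0.8, inclusion of baseline in the trajectory, 10% average dropout by month 24, and log-odds of leaving after each visit of a + b × (last observed score). Here exp(b) = 2 is the odds ratio per SD, and a is set to give the dropout rate. A higher score means more anxious.
- No true arm effect, 3,000 replicates, two-sided 5%, sandwich standard errors. Bias is 2 years × (Arm A slope − control slope per year), in SD units.

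**3. Results for GEE with working independence** (correlation 0.5 / 0.7 / 0.8).

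| Dropout, Arm A / control | Bias at 24 months (SD) | Type I error |
|---|---|---|
| 10% / 10%, unrelated to score | 0.00 | 4.5% / 5.4% / 5.1% |
| 10% / 10%, same dependence in both arms | 0.00 | 4.8% / 5.5% / 5.0% |
| 10% / 10%, dependence in control only | 0.034 / 0.049 / 0.058 | 6.0% / 10.1% / 16.2% |
| 5% / 15%, same dependence in both arms | 0.037 / 0.049 / 0.058 | 7.5% / 10.3% / 15.1% |
| 10% / 10%, opposite directions | 0.071 / 0.096 / 0.113 | 13.1% / 27.3% / 45.0% |

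**4. Check by hand.** For an approximately normal estimate, type I error = P(Z > 1.96 − d) + P(Z < −1.96 − d), where d = bias / SD of the estimate. In the control-only row:
- correlation 0.5: d = 0.034/0.088 = 0.39, error 6.7%
- correlation 0.7: d = 0.049/0.071 = 0.69, error 10.6%
- correlation 0.8: d = 0.058/0.064 = 0.91, error 14.8%

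These agree with the simulated 6.0%, 10.1% and 16.2%. The Monte Carlo standard error around a true 5% is √(0.05 × 0.95/3000) = 0.4 percentage points.

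**5. Direction.** The bias is positive: as anxious controls leave, the remaining controls look calmer and Arm A looks relatively worse.

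**6. The alternative.** On the same data, a random-intercept likelihood model had bias within about 0.002 SD and type I error of 4.5% to 6.2% at 10% average dropout. It was given the true covariance, which favours it. A separate, smaller run (209 per arm, 120 replicates) with an unstructured covariance estimated by maximum likelihood had bias of about 0.01 SD or less. When dropout depended on the unseen current score (150,000 men per arm, 10% dropout), the mixed model kept a bias of 0.01 to 0.06 SD, against 0.04 to 0.17 SD for the GEE.

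**The case against.** The strongest reply is that the documents do not describe the process that causes the bias. A control who chooses treatment out of anxiety is censored for progression but still owes his forms, because Section 8.7.3 keeps him in follow-up. The anxiety sentence in Section 11.3 concerns receiving treatment, not failing to return a questionnaire. Section 8.6.1 might be read as forecasting loss of interest in Arm A, but it describes management reports meant to ensure that "participants with lagging performance or possibly lagging interest do not drop out of the study". Reading the 10% as expected loss of forms, or reading differing reasons by arm as something that the plan states, goes beyond the text. If the arms lose similar men at similar rates, the comparison is unbiased even though neither trajectory is. Section 9.6 also calls the scores exploratory.

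All of this stands and limits the size and certainty of the point. It does not remove it. The rate and pattern of missing forms are unknown, and the chosen estimator is the one that offers no protection if they prove unfavourable. The exploratory label sits beside two secondary objectives that depend on the same scores, and the methods that go with that label do not use earlier scores for missing later ones either.

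**Conclusion.** The concern holds in a limited form. Under the assumptions listed, control-only or unequal score-dependent dropout biases the 24-month slope difference by about 0.03 to 0.06 SD and raises type I error to about 6% to 16%. The bias is small in absolute terms and is zero if the arms behave alike.

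Three stronger readings are not supported:
- **A false benefit of the diet.** The mechanism that the documents make plausible, anxious controls leaving, works against the diet and would mask a benefit.
- **Error rates of 13% to 45%.** These need dropout in opposite directions, with less anxious men leaving Arm A. Nothing in the documents suggests this.
- **A mixed model as a complete cure.** It is unbiased only under missing at random with an adequate mean and covariance model.

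The change is worth making because it is cheap and the replacement rests on a weaker assumption. The primary endpoint is not affected.

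**What to change.** - In Section 11.3, make a likelihood-based mixed model for repeated measures the main QOL analysis: all observed scores, visit as a category, arm-by-visit terms, unstructured covariance. A weighted GEE is an acceptable alternative.
- Keep the between-arm slope contrast and the multiplicity method. With arm differences d₀ to d₄ at the five visits, the 24-month slope difference is 0.4 × (−2d₀ − d₁ + d₃ + 2d₄).
- State the missing-data assumption, and report missing forms by arm, visit and reason.
- Add a sensitivity analysis for data missing not at random.
- Reconcile Section 9.6 with Section 11.3 on both the method and the status (secondary or exploratory) of these scores.

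The cost is SAP wording and standard software; no new scores are needed, although reasons for missing forms must be recorded. The downside is that a covariance model is needed, or a dropout model for weighted GEE. With five visits and 464 men, an unstructured covariance is feasible.
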